16.4. SENSITIVITY ANALYSIS OF EFFICACY VARIABLE(S)

No sensitivity or supportive analyses will be performed on efficacy variables.

17. SAFETY OUTCOMES

All outputs for safety outcomes except DLT summary will be based on the SAS. Safety data will be summarized by dose cohort in escalation phase and disease cohort in dose expansion phase.

17.1. ADVERSE EVENTS

An adverse event (AE) is any unfavorable and unintended sign, symptom, or disease temporally associated with the use of the investigational medicinal product or other protocol-imposed intervention, regardless of attribution. Relevant information is recorded on CRF page “Adverse Event/Serious Adverse Event”.

If a persistent AE becomes more severe, it should be recorded again with the updated severity. All recurrent AEs (AEs that occurs and resolves between patient evaluation time points and subsequently recurs) should be recorded on “Adverse Event/Serious Adverse Event” CRF.

[figure not shown]
A pre-existing medical condition should be recorded as an AE or SAE only if the frequency, severity, or character of the condition worsens during the study.

After informed consent, but prior to initiation of study medications, only SAEs caused by a protocol-mandated intervention will be collected.

After initiation of study medications, all AEs and SAEs regardless of attribution will be collected until 37 days (30 days + 7 days window) following the last administration of study medication or study discontinuation/termination, whichever is later. After this period, investigators should report only SAEs that are felt to be related to prior study treatment.

Treatment-emergent AEs (TEAEs) are defined as AEs that started or worsened in severity on or after the first administration date of study medication and no later than 30 (+7) days after the last administration date of study

CCI

medication or initiation of new anti-tumor therapy (whichever occurs first).

An exception is that study medication related SAEs collected later than 37 days after the last dosing date will be treated as TEAEs.

If the start date coincides with the reference start date, a query “Prior/ post 1st dose” will be used to identify TEAEs (only when ‘Post 1st dose’ will be considered as TEAE, if ‘Prior’ then not TEAE). When there is no definite answer to the query, the AE will be considered as a TEAE. See section 8.2 for handling of partial dates for AEs. In the case where it is not possible to classify an AE as treatment-emergent or not, the AE will be classified by the worst case; i.e. treatment-emergent.

If a subject reports a TEAE more than once in the SOC/PT, the TEAE with highest severity will be used in the corresponding summaries.

An overall summary of number of patients within each of the categories described in the sub-section below, will be provided for all AEs as specified in the templates.

For all SOC/PT summaries, AEs will be presented in alphabetic order except the uncoded SOC/PT. Uncoded SOC/PT will be presented as “Uncoded” and be presented at the end of relevant AE summaries.

A Listing of all AEs with relevant information being reported during study with flag to distinguish TEAE and Non-TEAE will be provided.

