5.1.2 Dose Expansion Phase

The expansion phase will evaluate the anti-cancer activity of surufatinib, and confirm the safety and tolerability of surufatinib at the RP2D determined at the end of the dose escalation phase.

Under amendment 7 of this protocol, the MTD was declared when 2 of the 6 DLT evaluable patients in Cohort 7 (400 mg QD dose) of the dose escalation phase reported DLTs. There was an ad hoc meeting of the SRC on 30 November 2018. The SRC agreed with the declaration of 300 mg QD as the MTD of surufatinib in this trial and agreed that 300 mg QD is the RP2D going forward. The minutes of this ad hoc SRC meeting were distributed to all investigative sites on the same day. It was also agreed that patients who were already receiving 400 mg QD could remain on this dose, provided that 1) there was no major toxicity and 2) the affected patients gave informed consent not to reduce the dose to 300 mg after discussion with the investigator. However, no patients could have their dose escalated to 400 mg going forward, including all patients in the dose expansion phase.

The safety of all enrolled patients will be closely monitored from the time of the initial dose of investigational treatment until 30 days after the last treatment dose. Any SAEs that occur after the informed consent form (ICF) is signed, but before the first dose of study drug is taken, should also be reported. All AEs will be graded in accordance with the NCI CTCAE v. 4.03. Tumor assessments will be conducted according to RECIST Version 1.1 criteria at screening, Cycle 2 Day 1 and every 8 (± 1) weeks thereafter. Confirmation of

CR and PR is required at no less than 4-week intervals between the date of initial response/progression and the confirmation assessment date.

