9.3 Adverse Events Reporting Period

After informed consent, but prior to initiation of study medications, only SAEs caused by a protocol-mandated intervention will be collected (eg, SAEs related to invasive procedures such as biopsies, medication washout, or no treatment run-in).

After initiation of study medications, all AEs and SAEs regardless of attribution will be collected until 30 days following the last administration of study drug or study discontinuation/termination, whichever is later. After this period, investigators should report only SAEs that are felt to be related to prior study drug.

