17.1.7. Deaths

If any patients die during the study conduct, as recorded on the “Death” CRF form, the count and cause of death and on treatment death (event occurs on or after first study medication dose and prior to 37 days [30 days + 7 days window] after the last dose) will be summarized by dose level in dose escalation phase, and by disease cohort in dose expansion phase.

Individual information of subject ID, death date and primary reason for death will be presented in the listing. On-treatment death will be flagged.

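### The SAP 17.1 exception for drug-related SAEs leaves a gap between the start of new anti-tumor therapy and day 37 after the last dose

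*SAP*

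**What the plan says.** SAP 17.1 defines a TEAE as an event that starts or worsens on or after the first dose and "no later than 30 (+7) days after the last administration date of study" "medication or initiation of new anti-tumor therapy (whichever occurs first"). One exception follows: "An exception is that study medication related SAEs collected later than 37 days after the last dosing date will be treated as TEAEs."

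Collection is not cut at new therapy. SAP 17.1 states that "all AEs and SAEs regardless of attribution will be collected until 37 days (30 days + 7 days window) following the last administration" or study discontinuation, whichever is later. Protocol 9.3 has the same structure with 30 days: events "will be collected until 30 days following the last administration of study drug or study discontinuation/termination, whichever is later." After that period, both documents ask only for SAEs felt to be related to the study drug.

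The incidence tables in SAP 17.1.1 (all TEAEs, by severity and by relationship), 17.1.4 (serious) and 17.1.5 (special interest) are built on TEAEs. Other events appear in the listing of all AEs, where a flag separates TEAE from non-TEAE. SAP 17.1.7 uses its own window for on-treatment deaths: "event occurs on or after first study medication dose and prior to 37 days" after the last dose, with no cut at new therapy.

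**The concern.** A cut at new anti-tumor therapy normally keeps events that may belong to the next treatment out of the study drug's tables. An exception for drug-related SAEs normally keeps the events that matter most, whenever they occur. Here the two do not fit together. The exception begins at day 37 even when the window closed earlier, so related SAEs near the last dose can be left out while later ones, after longer exposure to the next therapy, are kept. The documents give no reason for this ordering. The exception appears to follow the end of routine collection rather than the end of the TEAE window.

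At stake are the counts of related and serious TEAEs and of TEAESIs. Only patients who start another therapy within 37 days of the last dose can be affected.

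**Working it through.** No sample-size or power figure is involved, and the plan gives no number to reproduce. The check applies the rule as written. Days are counted from the last dose, and *d* is the day on which new anti-tumor therapy starts.

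**Rule on the ordinary reading**
- TEAE if onset ≤ min(37, *d*), from the window sentence in SAP 17.1.
- Also a TEAE if it is a related SAE later than day 37, from the exception in SAP 17.1.

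**A related SAE when new therapy starts on day 14**

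| Onset day | Within min(37, 14) = 14? | Later than 37? | TEAE? |
|---|---|---|---|
| 5 | yes | no | yes |
| 20 | no | no | **no** |
| 30 | no | no | **no** |
| 37 | no | no | **no** |
| 38 | no | yes | yes |
| 40 | no | yes | yes |

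**Length of the gap.** For *d* below 37 the uncounted days run from *d* + 1 to 37, so the gap is 37 − *d* days. The start days below are illustrations, since the documents give none.

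| New therapy starts | Uncounted onset days | Gap |
|---|---|---|
| day 7 | 8–37 | 37 − 7 = 30 |
| day 10 | 11–37 | 37 − 10 = 27 |
| day 14 | 15–37 | 37 − 14 = 23 (23/37 = 62% of the window) |
| day 21 | 22–37 | 37 − 21 = 16 (16/37 = 43%) |
| day 28 | 29–37 | 37 − 28 = 9 |
| none, or day 37 or later | none | 0 |

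A day-20 event is therefore excluded only if new therapy began before day 20.

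**Collected versus started.** The window sentence goes by onset, but the exception goes by collection. Take new therapy on day 10 and a related SAE with onset on day 20. If the site reports it by day 37, it is not a TEAE. If it is first collected on day 45, the literal exception makes it one. Inclusion then depends on reporting delay.

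**Does other text close the gap?** The worst-case rule in SAP 17.1 applies only when an event cannot be classified. Here the dates are known and the rule gives a definite answer. The protocol contains no TEAE definition that would override the SAP.

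**Deaths.** With new therapy on day 14, a related SAE with onset on day 20 and death on day 25 is an on-treatment death under 17.1.7, but not a Grade 5 or serious TEAE under 17.1.

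**The case against.** **Another parse.** The strongest objection is grammatical. The window sentence can also mean 37 days after the earlier of last dose and new therapy. On that reading, therapy started after the last dose shortens nothing and the gap disappears. The reading is possible but leaves the new-therapy clause almost no work. SAP 8.2 expects subsequent therapy to start after end of treatment or progression, and SAP 14 treats concurrent oncology therapy as a deviation, so the last dose would nearly always come first. The ordinary reading gives the clause an effect and creates the gap. That two readings exist is itself a reason to reword.

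**Loss of data.** A reader might infer that these SAEs vanish. They do not: they are collected, flagged as SAEs and listed as non-TEAE. Fatal ones inside the 17.1.7 window also appear in the death summary. They are missing from the incidence tables only.

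**Number of patients.** It is tempting to assume a switching rate and quote a number of patients. The documents give no such rate, and the result would count shortened windows, not missed SAEs. A miss needs a related SAE with onset inside the gap.

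**Conflicting collection periods.** A reader might infer that the protocol and SAP set irreconcilable closing days. They do not. Both Protocol 9.3 and SAP 17.1 say whichever is later, and the SAP's 37 days is the protocol's 30 plus the visit window. Protocol 5.1.2, with "until 30 days after the last treatment dose," describes safety monitoring and does not limit AE collection. What stands is a minor 30-versus-37-day wording difference.

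**RP2D.** The RP2D is untouched. It was declared on 30 November 2018 from Cycle 1 DLTs (Protocol 5.1.1 and 5.1.2). Safety in the expansion phase is a secondary, descriptive endpoint.

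**Conclusion.** The point holds on the ordinary reading of SAP 17.1. When new anti-tumor therapy starts on day *d* before day 37, related SAEs with onset in the following 37 − *d* days are left out of the TEAE, serious TEAE and TEAESI tables, while later ones are counted. The gap is 23 days for a start on day 14 and 16 days for a start on day 21; both start days are illustrative. The number of SAEs affected is unknown and may be small or zero. The direction is clear: the rule can only lower the count of related serious TEAEs in patients who move quickly to another treatment.

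A reader might also conclude that the death table and the Grade 5 TEAE table ought to agree. The documents do not require that. One goes by date of death and the other by onset of the event, so they can legitimately differ. The difference needs explaining, not removing.

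This should be settled before database lock. It affects safety reporting, not the dose decision or the primary endpoints.

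**What to change.** 1. Replace the exception in SAP 17.1 with: *SAEs related to study medication with onset on or after the first dose are TEAEs regardless of time since last dose or start of new anti-tumor therapy.* The gap becomes 0 days for every *d*, and the dependence on collection date goes.
2. Reword the window sentence so that it has one reading, for example: *the window closes on the earlier of (a) day 37 after the last dose and (b) the day new anti-tumor therapy starts.*
3. Footnote the death and Grade 5 tables to say that on-treatment deaths (17.1.7) and Grade 5 TEAEs (17.1) use different windows. Do not move all on-treatment deaths into the Grade 5 table. Protocol 9.12 records progression deaths in the reporting period as AEs, so the move would bring unrelated progression deaths on a later therapy into the study drug's TEAE counts.
4. Reconcile the 30-day (Protocol 9.3) and 37-day (SAP 17.1) closing days when either text is next edited.

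The main change costs one SAP sentence and one programming condition; the rest is wording. The downside is a few more serious TEAEs, some partly attributable to the next therapy.

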17.1.1. All TEAEs

In the analysis of AEs, the MedDRA adverse event dictionary Version 23.0 or higher will be used to map verbatim terms to SOC and PT.

An overall summary of TEAEs including severity, relationship, action taken, and outcome will be provided.

Incidence of TEAEs will be presented by SOC and then PT and also broken down further by maximum severity (Section 17.1.1.1) and relationship to study medication (Section 17.1.1.2) for each dose level, and each disease cohort. Number (n) and percentage (%) will be presented with the % calculated relative to the total number of patients in the SAS. In the case that a patient report multiple TEAEs, the TEAE with worst severity and strongest relationship (related to study medication) will be used in the corresponding summaries.

17.1.1.1 Severity

The severity of all TEAEs will be graded according to 5 grades (Grade 1 to Grade 5) in accordance with the National Cancer Institute Common Terminology criteria for adverse events (NCI-CTCAE) V4.03 as defined in the Study Protocol Section 7.1.5.

TEAEs missing severity will be classified as Grade 3.

TEAEs of each severity grade will be summarized using incidence (frequencies and percentages) by SOC and PT will be summarized by dose level in the dose escalation phase and by disease cohort in the dose expansion phase. If

CCI

a patient reports a TEAE more than once within that SOC/ PT, the AE with the worst case severity will be used in the corresponding severity summaries.

17.1.1.2 Relationship to Study Medication

As indicated by the Investigator, causal relationship between AEs and study medication will be classified as “reasonably possible” or not. TEAEs with missing relationship to study medication will be regarded related. Related and Not Related TEAEs will be summarized by dose level in dose escalation phase, and by disease cohort in dose expansion phase using incidence (frequencies and percentages) by SOC and PT. If a patient reports the same AE more than once within that SOC/ PT, the AE with the worst relationship (ie, related) to study medication will be used in the corresponding relationship summaries.

17.1.2. TEAEs Leading to Discontinuation of Study Medication

TEAEs leading to permanent discontinuation of study medication will be identified as those records with a response of “Drug Withdrawn” to the item “Action taken with the study drug” on the “Adverse Event/Serious Adverse Event (AE/SAE)” form of the CRF.

For TEAEs leading to drug discontinuation, summaries of incidence (frequencies and percentages) by SOC and PT will be prepared. Summaries for TEAEs leading to discontinuation of study medication by SOC and PT will be further broken down by maximum severity and relationship to study medication.

17.1.3. TEAEs Leading to Study Medication Adjustment

TEAEs leading to study medication adjustment will be identified as those records with a response of “Drug interrupted” or “Dose reduced” or ‘Dose increased’ to the item “Action taken with the study drug” on the AE/SAE form of the CRF.

For TEAEs leading to study medication adjustment, summaries of incidence (frequencies and percentages) by SOC and PT will be prepared. Summaries for TEAEs leading to study medication adjustment by SOC and PT will be further broken down by maximum severity and strongest relationship to study medication.

17.1.4. Serious TEAEs

A serious adverse event (SAE) is defined as any life-threatening AE resulting in death, persistent or significant disability/incapacity, a congenital anomaly/birth defect, or any other important medical event requiring intervention, in-patient hospitalization or prolongation of existing hospitalization.

Detailed definition of SAEs can be found in Protocol Section 9.1.1.

On the CRF, SAEs are those events with a response of “Yes” for the item “Does the Adverse Event meet seriousness criteria?”. Summaries of incidence (frequencies and percentages) of serious TEAEs by SOC and PT will be

CCI

prepared. In addition, summaries for serious TEAEs by SOC and PT will be further broken down by maximum severity and strongest relationship to study medication.

SAEs will be flagged and included in a listing of AEs.

17.1.5. TEAEs Of Special Interest (TEAESI)

The preferred terms for TEAESI are included in Appendix 2. Summaries of incidence (frequencies and percentages) of TEAESIs by Standardized MedDRA Queries (SMQ) and PT based on the [Appendix 2](#) will be prepared. The broad search will be used for SMQ terms. Time to TEAESI onset is defined as time interval from date of first administration of study medication to the earliest onset date among TEAEs within the same SMQ. Time to TEAESI onset will be summarized by SMQ for each dose cohort and disease cohort.

AESIs will be flagged and included in a listing of AEs.

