3.3 Benefit and Risk Assessment

Based on the available non-clinical and clinical data, identified risks of surufatinib include hepatic disorders, proteinuria, hypertension, myelosuppression, haemorrhage, and acute kidney injury. Potential risks include infection, intestinal obstruction, myocardial

ischaemia, cardiac failure, thromboembolism, pancreatitis, GI perforation, and posterior reversible encephalopathy syndrome. These are further described in the surufatinib IB.

Appropriate exclusion criteria, monitoring, and dose modification guidance are included in the protocol to ensure the safety of patients enrolled in the clinical trial. Patients are excluded if they have signs, symptoms, or history that may put them at risk in the context of the identified and potential risks of surufatinib including abnormal serum total bilirubin or ALT/AST or other signs of hepatic damage; urine protein $\geq 2+$; uncontrolled hypertension; abnormal neutrophil count, platelet count, or haemoglobin level; signs of risk of haemorrhage; creatinine clearance <60 mL/min; conditions that could possibly result in gastrointestinal tract hemorrhage or perforation; clinically significant cardiovascular disease; history of thromboembolic events; and posterior reversible encephalopathy syndrome (PRES). Patients with other disease, metabolic disorder, physical examination abnormality, abnormal laboratory result, or any other condition that investigators suspect may prohibit use of the investigational product, affect interpretation of study results, or put the patient at high risk are also excluded.

[Section 7.2.3](#) provides detailed guidance on dose modifications for important identified risks including hypertension, proteinuria, liver function and haemorrhage, and general dosing guidance to protect subjects are included in [Section 7.2.2](#). Thus, the identified and potential risks of treatment with surufatinib are appropriately mitigated by measures in the protocol.

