9.8 Diagnosis vs Symptom and Signs

If known, a diagnosis should be recorded on the CRF rather than individual signs and symptoms (eg, record only liver failure or hepatitis rather than jaundice, asterixis, and elevated transaminases). However, if a constellation of signs and/or symptoms cannot be medically characterized as a single diagnosis or syndrome at the time of reporting, each individual event should be recorded as an AE or SAE on the CRF. If a diagnosis is subsequently established, it should be reported as follow-up information.

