9.11 Abnormal Laboratory Values

Only clinically significant laboratory abnormalities that require active management will be recorded as AEs or SAEs on the CRF (eg, abnormalities that require study drug dose modification, discontinuation of study drug, more frequent follow-up assessments, further diagnostic investigation, etc).

If the clinically significant laboratory abnormality is a sign of a disease or syndrome (eg, alkaline phosphatase and bilirubin $5 \times$ ULN associated with cholecystitis), only the diagnosis (eg, cholecystitis) needs to be recorded on the AE/SAE CRF.

If the clinically significant laboratory abnormality is not a sign of a disease or syndrome, the abnormality itself should be recorded as an AE or SAE on the CRF. If the laboratory abnormality can be characterized by a precise clinical term, the clinical term should be recorded as the AE or SAE. For example, an elevated serum potassium level of 7.0 mmol/L should be recorded as “hyperkalemia.”

Observations of the same clinically significant laboratory abnormality from visit to visit should not be repeatedly recorded as AEs or SAEs on the CRF, unless their severity, seriousness, or etiology changes.

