APPENDIX 2. ADVERSE EVENTS OF SPECIAL INTEREST

AESI SMQ	PT Term	PT Code
Acute renal failure	Acute kidney injury	10069339
	Acute phosphate nephropathy	10069688
	Anuria	10002847
	Azotaemia	10003885
	Continuous haemodiafiltration	10066338
	Dialysis	10061105
	Foetal renal impairment	10078987
	Haemodialysis	10018875
	Haemofiltration	10053090

CCI

	Neonatal anuria	10049778
	Nephropathy toxic	10029155
	Oliguria	10030302
	Peritoneal dialysis	10034660
	Prerenal failure	10072370
	Renal failure	10038435
	Renal failure neonatal	10038447
	Renal impairment	10062237
	Renal impairment neonatal	10049776
	Subacute kidney injury	10081980
Haemorrhages	Abdominal wall haematoma	10067383
	Abdominal wall haemorrhage	10067788
	Abnormal withdrawal bleeding	10069195
	Achenbach syndrome	10079562
	Acute haemorrhagic leukoencephalitis	10058994
	Acute haemorrhagic ulcerative colitis	10075634
	Administration site bruise	10075094
	Administration site haematoma	10075100
	Administration site haemorrhage	10075101
	Adrenal haematoma	10059194
	Adrenal haemorrhage	10001361
	Anal fissure haemorrhage	10079765
	Anal haemorrhage	10049555
	Anal ulcer haemorrhage	10063896
	Anastomotic haemorrhage	10056346
	Anastomotic ulcer haemorrhage	10002244
	Aneurysm ruptured	10048380
	Angina bullosa haemorrhagica	10064223
	Anorectal varices haemorrhage	10068925
	Anticoagulant-related nephropathy	10083346
	Aortic aneurysm rupture	10002886
	Aortic dissection rupture	10068119
	Aortic intramural haematoma	10067975
	Aortic perforation	10075729
	Aortic rupture	10060874
	Aponeurosis contusion	10075330
	Application site bruise	10050114
	Application site haematoma	10068317
	Application site haemorrhage	10072694
	Application site purpura	10050182
	Arterial haemorrhage	10060964
	Arterial intramural haematoma	10074971
	Arterial perforation	10075732
	Arterial rupture	10003173
	Arteriovenous fistula site haematoma	10055150
	Arteriovenous fistula site haemorrhage	10055123
	Arteriovenous graft site haematoma	10055152

CCI

Arteriovenous graft site haemorrhage	10055126
Astringent therapy	10067372
Atrial rupture	10048761
Auricular haematoma	10003797
Basal ganglia haematoma	10077031
Basal ganglia haemorrhage	10067057
Basilar artery perforation	10075736
Bladder tamponade	10062656
Bleeding varicose vein	10005144
Blood blister	10005372
Blood loss anaemia	10082297
Blood urine	10005863
Blood urine present	10018870
Bloody discharge	10057687
Bloody peritoneal effluent	10067442
Bone contusion	10066251
Bone marrow haemorrhage	10073581

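### Adding creatinine, clearance and GFR terms to the renal AESI group, and one once-per-patient hepatic row, would cheaply improve the AESI summaries

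*SAP*

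**What the plan says.** SAP 17.1.5 fixes the AESI terms by list: "The preferred terms for TEAESI are included in Appendix 2". It adds "The broad search will be used for SMQ terms". Incidence is tabulated by Standardised MedDRA Query (SMQ) group and preferred term (PT). Time to onset runs from first dose to the "earliest onset date among TEAEs within the same SMQ". AESIs are also flagged in the adverse event listing.

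In Appendix 2 the renal group is *Acute renal failure*. It runs alphabetically from *Acute kidney injury* to "Subacute kidney injury", after which the haemorrhage group begins. The liver is spread over four groups: cholestasis and jaundice; failure, fibrosis and cirrhosis; non-infectious hepatitis; and liver-related investigations, signs and symptoms.

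Protocol 3.3 shows why both organs matter: "identified risks of surufatinib include hepatic disorders, proteinuria, hypertension, myelosuppression, haemorrhage, and acute kidney injury".

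Three recording rules decide which term reaches the database:
- Protocol 9.11, on when a laboratory finding is recorded at all: "Only clinically significant laboratory abnormalities that require active management will be recorded as AEs or SAEs on the CRF".
- Protocol 9.11, where the finding is not a sign of a disease or syndrome: "the abnormality itself should be recorded as an AE or SAE on the CRF", with a precise clinical term used if there is one.
- Protocol 9.8: "If known, a diagnosis should be recorded on the CRF rather than individual signs and symptoms".

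**The concern.** Kidney injury often first shows as a creatinine rise. If that rise leads to a dose hold or closer follow-up and no diagnosis is assigned, Protocol 9.11 makes the laboratory finding the adverse event. The renal AESI list has no term to receive it. The matching event for the liver, blood pressure, urine protein or thyroid would be caught. Renal AESI incidence could then be understated. Onset could also be late in a patient whose creatinine event came before a listed renal diagnosis.

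The hepatic question is separate. The protocol names hepatic disorders as one risk, but the SAP reports it in four overlapping groups and defines onset within a group. The planned rows do not show how many patients had any hepatic AESI, or when the first one occurred.

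Only the safety display is at stake. No endpoint, decision or dataset changes.

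**Working it through.** The documents state no count of AESI terms, so there is no plan figure to reproduce. The counts below come from the printed Appendix 2.

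**1. Result-type terms by group.** A term is called result-type here if its name contains increased, decreased, abnormal, present, absent or positive. This is a working definition, not the SAP's.

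| Group | Result-type / all PTs |
|---|---|
| Acute renal failure | 0 / 19 |
| Cholestasis and jaundice | 1 / 15 |
| Hepatic failure, fibrosis, cirrhosis | 0 / 86 |
| Hepatitis, non-infectious | 0 / 20 |
| Liver investigations, signs, symptoms | 48 / 74 |
| Hypertension | 6 / 53 |
| Proteinuria | 8 / 16 |
| Thyroid dysfunction (visible part) | 45 / 105 |

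The renal group is built like the liver's diagnosis groups. The difference is that the liver also has an investigations group and the kidney has none. In the groups tabulated, the only terms containing the word creatinine are three urine-ratio terms under Proteinuria. Those measure protein leak, not loss of renal function.

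**2. Following one event through the rules.** A creatinine rise needs active management and no diagnosis or precise clinical term is assigned. Protocol 9.11 makes the finding the adverse event, and it codes to a creatinine term. That term is not in Appendix 2, so the event enters neither renal AESI incidence nor onset and is not flagged. It still appears in the all-TEAE tables by system organ class (SOC) and PT, and the values appear in the laboratory shift tables (SAP 17.2). If the investigator instead records acute kidney injury or renal impairment, it is counted.

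**3. Renal size.** The number of missed patients cannot be derived from the documents. One missed patient is 1/15 = 6.7%, 1/30 = 3.3% or 1/55 = 1.8% of an arm. For scale, Protocol 2.3 lists acute kidney injury among SAEs with a frequency of at least 1%. At a counted renal rate of 1%, the expected counts are 0.01 × 15, 30, 55 = 0.15, 0.30, 0.55 patients. At an assumed 10% they are 1.5, 3.0 and 5.5.

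**4. Hepatic overlap.** Entries: 15 + 86 + 20 + 74 = 195. Shared PTs, each in exactly two groups: cholestasis–failure 3, cholestasis–hepatitis 1, cholestasis–investigations 1, failure–hepatitis 3, failure–investigations 6, hepatitis–investigations 0; total 14. Distinct PTs: 195 − 14 = 181. For example, *Hyperbilirubinaemia* falls in two groups, while *Blood bilirubin increased* falls in one.

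**5. Hepatic size.** The any-hepatic rate lies between the largest row and the sum of the rows. Protocol 2.3 reports raised bilirubin and raised AST each as treatment-related in at least 20% of 714 patients, and both PTs sit only in the investigations group. If that rate holds here (assumed), the row has at least 0.20 × 15, 30, 55 = 3, 6, 11 patients. If the other three rows are 1% each (the floor given for cholestatic jaundice SAEs, assumed for all three), the any-hepatic rate exceeds the largest row by 0 to 3 × 1 = 3 points. At an assumed 5% each, it exceeds it by 0 to 3 × 5 = 15 points.

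**The case against.** The strongest case is that this is a preference about list content. The named risk is acute kidney injury, and the group contains that term along with renal failure, renal impairment, azotaemia and oliguria. Protocol 9.8 and 9.11 steer investigators to a diagnosis or precise term, so few events, perhaps none, would be missed. Other groups are also mainly diagnosis-type: two liver groups have no result-type term, and the haemorrhage group is almost wholly diagnoses. The creatinine clearance exclusion is a baseline eligibility rule and implies nothing about AESI content. Creatinine is already analysed by visit and by CTCAE grade shift, and clearance is derived. All of this stands, and it limits the size. It does not give an undiagnosed creatinine event a place in the renal AESI group.

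A reader might infer that the list contradicts the broad-search sentence. The documents do not support that: MedDRA's content is not in them, so they cannot show which terms a broad renal search would return.

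A reader might also infer that the hepatic rows double-count patients. They do not. No text adds the rows, and separate rows for overlapping SMQs are legitimate. Nor is a once-per-patient count missing in general. SAP 17.1 plans patient counts by adverse event category, which can give any AESI; the gap concerns only the hepatic union. Because AESIs are flagged, that union can be programmed.

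Finally, the output templates and anything in Appendix 2 beyond the visible thyroid list were not available. A pooled hepatic row or a further renal group there cannot be excluded, although the printed renal list looks complete.

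**Conclusion.** The point holds as a cheap improvement to safety reporting, not as an error. As printed, the renal AESI group cannot receive a managed creatinine, clearance or GFR event that has no diagnosis, while four other AESI areas list result-type terms. The effect on renal incidence and onset is unknown in size and may be nil. The hepatic part is secondary: the four SMQ rows are not wrong, but they cannot give the share of patients with any hepatic AESI or the time to the first one.

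This rests on taking the printed list as operative and on the visible text being complete on these two points. The percentages use planned arm sizes of 15, 30 and 55. SAP section 6 pools same-tumour escalation patients treated at the RP2D, so actual denominators may be larger and each patient's weight smaller. The 5% and 10% rates, and carrying the pooled-database floors over to these arms, are assumptions.

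**What to change.** In Appendix 2, add the PTs for increased creatinine, decreased creatinine clearance and decreased GFR to the renal group, with exact names and codes taken from the MedDRA version in use. In SAP 17.1.5, add one row for any hepatic disorder that counts each patient once over the four hepatic groups, with time to first onset computed on their union. Keep the four SMQ rows.

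The cost is three terms and one derived row, with no new data. The downside is a slightly higher and less specific renal AESI rate; the PT rows would show how much of it comes from the added terms.
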